### **8.8.2 Planned Genetic Analysis Sample Collection**

The sample for genetic analysis should be drawn for planned exploratory biomarker research. This sample will not be collected at the site if there is either a local law or regulation prohibiting collection, or if the IRB/IEC does not approve the collection of the sample for these purposes. If the sample is collected, leftover extracted DNA will be stored for future biomedical research if the participant signs the future biomedical research consent. If the genetic sample collection is not approved, but future biomedical research is approved and consent is given, this sample will be collected for the purpose of future biomedical research.

### **8.9 Future Biomedical Research Sample Collection**

If the participant signs the future biomedical research consent, the following specimens will be obtained as part of future biomedical research:

- DNA for future research
- Leftover plasma and serum from biomarker analyses
- Leftover DNA and RNA
- Leftover tumor tissue, including tumor cell lines
- Leftover sorted single cells and PBMCs

## **8.10 Visit Requirements**

Visit requirements are outlined in Section 1.3. Specific procedure-related details are provided above in Section 8.

### **8.10.1 Screening**

Written consent must be obtained prior to performing any protocol-specific procedure. Results of a test performed prior to the participant signing consent as part of routine clinical management are acceptable in lieu of a screening test if performed within the specified time frame. Screening procedures are to be completed within 28 days prior to the first dose of study treatment except for the following:

- Consent Form signed within 42 days. The consent form must be signed prior to completing any protocol protocol-specified procedure.
- Laboratory tests and evaluation of ECOG status are to be performed within 10 days prior to the first dose of study treatment
- For women of reproductive potential, a urine pregnancy test will be performed within 72 hours prior to the first dose of study treatment. If urine pregnancy results cannot be confirmed as negative, a serum pregnancy test will be required (performed by the local study site laboratory)

Participants may be rescreened after initially failing to meet the inclusion/exclusion criteria. Results from assessments during the initial screening period are acceptable in lieu of a repeat screening test if performed within the specified time frame and the corresponding inclusion/exclusion criteria is met. Participants who are rescreened will retain their original screening number.

### **8.10.2 Treatment Period**

Visit requirements are outlined in Section 1.3. Specific procedure-related details are provided above in Section 8.1.

### **8.10.3 Poststudy**

#### **8.10.3.1 Safety Follow-up Visit**

The mandatory Safety Follow-up Visit should be conducted approximately 30 days after the last dose of study treatment or before the initiation of a new anticancer treatment, whichever comes first.

All AEs that occur prior to the Safety Follow-Up Visit should be recorded. Participants with an AE of Grade >1 will be followed until the resolution of the AE to Grade 0-1 or until the beginning of a new anticancer therapy, whichever occurs first. Serious AEs that occur within 90 days of the end of treatment or before initiation of a new anticancer treatment should also be followed and recorded.

### **8.10.3.2 Follow-up Visits**

Participants who discontinue trial treatment for a reason other than disease progression will move into the Follow-Up Phase and should be assessed every 9 weeks (63 days  $\pm$ 7 days) during the first year (52 weeks) and every 12 weeks (84 days  $\pm$ 7 days) thereafter, by radiologic imaging to monitor disease status. Every effort should be made to collect information regarding disease status until the start of new anti-cancer therapy, disease progression, death, or end of study. Information regarding post-study anticancer treatment will be collected if new treatment is initiated.

### **8.10.3.3 Survival Follow-up**

Participants who experience confirmed disease progression or start a new anticancer therapy, will move into the Survival Follow-Up Phase and should be contacted by telephone approximately every 12 weeks to assess for survival status until death, withdrawal of consent, or the end of the trial, whichever occurs first.

### **8.10.3.4 Survival Status**

To ensure current and complete survival data is available at the time of database locks, updated survival status may be requested during the course of the study by the Sponsor. For example, updated survival status may be requested prior to but not limited to an external Data Monitoring Committee (eDMC) review, interim and/or final analysis. Upon Sponsor notification, all participants who do not/will not have a scheduled study visit or study contact during the Sponsor defined time period will be contacted for their survival status (excluding participants that have a previously recorded death event in the collection tool).

## **9. Statistical Analysis Plan**

This section outlines the statistical analysis strategy and procedures for the study. Changes to analyses made after the protocol has been finalized, but prior to final database lock, will be documented in a supplemental statistical analysis plan (sSAP) and referenced in the Clinical Study Report (CSR) for the study. Post hoc exploratory analyses will be clearly identified in the CSR. Details around the analysis approach for biomarker endpoints related to the secondary and exploratory objectives are deemed out of scope for this SAP, but may be the subject of sSAPs.

## 9.1 Statistical Analysis Plan Summary

Key elements of the statistical analysis plan are summarized below; the comprehensive plan is provided in Sections 9.2 through 9.12.

Study Design Overview	This is a single-arm, open label, trial of pembrolizumab in participants with advanced melanoma.
Treatment Assignment	All participants will receive pembrolizumab at a dose of 200 mg Q3W by non-random assignment in an unblinded fashion.
Analysis Populations	Primary objectives: The All Participants as Treated (APaT) population will be used as the analyses population for primary objectives. Efficacy objective (secondary objective): APaT population. Safety: APaT population.
Primary Endpoints	1. Fraction of cytotoxic tumor-infiltrating T-lymphocytes (FCT) at baseline. 2. FCT fold change from baseline. 3. Average Specific Cytotoxic T-lymphocyte Frequency Ratio (ASCTFR)
Key Secondary Endpoints / Variables	1. Objective response rate (ORR) by RECIST 1.1 (investigator-assessed). 2. Progression-free-survival (PFS) by RECIST 1.1 (investigator-assessed). 3. Overall survival (OS). 4. Safety measures
Statistical Methods for Key Biomarker Analyses	The primary objectives will be evaluated by estimating the posterior distribution of the difference in means of the primary endpoints for responders vs. non-responders via the Bayesian framework.
Statistical Methods for Key Efficacy Analyses	The secondary efficacy objective will be evaluated by reporting summary statistics and 95% confidence intervals for ORR (with Clopper-Pearson CI), PFS, and OS (via Kaplan-Meier method).
Statistical Methods for Key Safety Analyses	Descriptive summary statistics will be provided as appropriate.
Interim Analyses	Interim analyses that will not change the conduct of the study may be performed during the course of the study.  Final analyses: the final analyses will be carried out after all participants have had a 90-day follow-up after the end of treatment (unless lost to follow-up). If by that time the death rate is <70%, for OS and OS-related analyses, the final analyses will occur after death has occurred in approximately 70% of the subjects (~42 deaths). If the estimated interval between the 2 analyses is less than 3 months, then the first analysis may be delayed and both analyses will be conducted at the later of the two.
Multiplicity	No multiplicity adjustment will be applied.
Sample Size and Power	The study will enroll approximately 60 participants. If there are at least 10 responders, reasonable power supporting the primary objectives can be expected (~90% power for baseline FCT with a mean difference of 0.10; ~80% power for FCT fold-change from baseline with an effect size of 0.50 on natural log scale; and ~80% power for ASCTFR with an effect size of 0.50).

## 9.2 Responsibility for Analyses/In-house Blinding

The statistical analysis of the data obtained from this study will be conducted by, or under the direct auspices of, the Early Clinical Development Statistics Department in collaboration with Genetics and Pharmacogenomics Department of the Sponsor.

This trial is being conducted as an open-label study, i.e., participants, investigators, and Sponsor personnel will be aware of participant treatment assignments after each participant is enrolled and treatment is assigned.

Biomarker assays used to assess the primary, secondary and exploratory objectives in this study will be performed by personnel blinded to participants' clinical outcome data, as appropriate, in order to preserve an objective evaluation of the study objectives. Separation between the generation of the biomarker data and knowledge of clinical outcome will permit a flexible assessment strategy for the complex biomarker data without impinging on the validity of the eventual comparison between responders and non-responders. If deemed appropriate, clinical outcome data of a subset of participants may be unblinded to certain biomarker personnel(s) and these data will be used as a testing dataset to generate specific hypotheses surrounding the biomarker data. These additional hypotheses will be tested in the corresponding validation dataset (i.e., participants not part of the testing dataset). If this testing and validation strategy is utilized, additional details will be provided in the sSAP prior to implementation.

Interim analyses and timing of the final analyses are described in Section 9.7.

## 9.3 Hypotheses/Estimation

Objectives of the study are stated in Section 3.

## 9.4 Analysis Endpoints

Biomarker, efficacy, and safety endpoints that will be evaluated are outlined in the following sections.

### 9.4.1 Biomarker Endpoints

#### 9.4.1.1 Primary Biomarker Endpoints

The primary intra-tumoral biomarker measures that will be compared between responders and non-responders in evaluation of the primary objectives are

- 1) FCT, defined as the fraction of cytotoxic CD8+ T-cells expressing a predefined single-cell RNA gene signature to the total tumor infiltrating CD8+ T-cells isolated from tumor biopsies.

To quantify FCT based on scRNAseq data we will use a previously defined signature of cytotoxic T-cells [Tirosh, I., et al 2016]. RNAseq reads will be used to assemble TCR and B-cell receptor sequences and then identify T-cell or B-cell clones. Dimensionality reduction and graph clustering will then be used to partition cell types by their expression profiles and associate them with cell-specific signatures. Statistical scoring will be adapted for single cell data to identify key cell states and their respective signatures, within and across cell types (e.g., phases of the cell cycle, inflammation, activation states, "activation-independent

exhaustion, drug resistance signatures). The cell type and state signatures will be compared to a large and diverse set of immune cells from various cancer cohorts [Tirosh, I., et al 2016] [Venteicher, A. S., et al 2017] [Zheng, C., et al 2017]. T-cells with an overall high expression of the cytotoxic signature will be defined as cytotoxic tumor-infiltrating T-lymphocytes. A cytotoxic score will be calculated for each cell to quantify the expression level of the cytotoxic signature (details in next paragraph). If the cells' cytotoxic score has a bimodal distribution, a natural cutoff will define highly cytotoxic T-cells. If it is not bimodal, we will define an “artificial” cutoff using the continuous scores (e.g., 90th percentile). The FCT will be calculated as the relative abundance of these cells compared to the overall number of sequenced CD8+ T-cells, i.e., the number of cytotoxic CD8+ T-cells (with high cytotoxic scores) divided by the number of total CD8+ T-cells that were sequenced in this tumor.

To calculate the cytotoxic score, genes will be binned into 50 *expression bins* according to their average expression across CD8+ T-cells. Let  $T_{ij}$  be the normalized expression of gene  $i$  in cell  $j$ . Let  $\mathbf{S}$  be the gene signature of the cytotoxic T-cells, and  $\tilde{\mathbf{S}}$  a random signature with the same distribution of genes across the *expression bins* as  $\mathbf{S}$ . The cytotoxic score ( $CytS$ ) of a cell is defined as:

$$CytS_j = \frac{\sum_{i \in S} T_{ij}}{E[\sum_{i \in \tilde{S}} T_{ij}]}$$

- 2) FCT fold-change from baseline, and
- 3) Average Specific Cytotoxic T-lymphocyte Frequency Ratio (ASCTFR): defined as the arithmetic mean of log10 ratio of the frequency of individual specific cytotoxic TCR clones on-treatment to pre-treatment (baseline). In this definition, pre-treatment frequencies of unique (as determined by TCR V $\beta$  chain sequencing) specific cytotoxic clones will be used to normalize the on-treatment frequencies. Each participant's ASCTFR will then be calculated as the arithmetic mean of the log10 ratios of the on-treatment to pre-treatment frequencies across the unique specific cytotoxic clones identified within that participant. For example, consider one participant who has two specific cytotoxic TCR clones, Clone A and Clone B, and for each of these two clones the participant has pre-treatment frequency measurements A0/B0 and on-treatment frequency measurements A1/B1, then the ASCTFR for this participant will be calculated as:

$$ASCTFR = \frac{\log_{10}\left(\frac{A1}{A0}\right) + \log_{10}\left(\frac{B1}{B0}\right)}{2}$$

The specific TCR clones will be selected based on their frequency as well as the interferon- $\gamma$  signature. Here the frequency is in reference to the specific tumor-infiltrating lymphocyte TCR V $\beta$  frequency distribution (obtained by TCR deep sequencing) in the pre-treatment and on-treatment biopsies. The cytolytic function of these TCR clones will be determined based on  $CytS$  obtained from the scRNAseq (as used in the definition of FCT).

#### **9.4.1.2 Secondary and Exploratory Biomarker Endpoints**

Details around other biomarker related endpoints associated with secondary and exploratory objectives, including tumor-associated epitopes, the pipeline surrounding the identification of neoepitopes, what will define the response of T-cell clones to such epitopes, as well as details for the processing and normalization of the complex data sources to be generated by the set of methods described in Section 4.2.1.3 are deemed out of scope for this SAP, but will be described in the CSR and may be the subject of sSAPs.

#### **9.4.2 Efficacy Endpoints**

##### **Secondary Efficacy Endpoints**

- 1) ORR is defined as the proportion of the participants in the analysis population who have a best response as CR or PR. Responses are based on local site review using RECIST 1.1.
- 2) PFS is defined as the time from start of treatment to the first documented PD (based on local site review using RECIST 1.1) or death due to any cause, whichever occurs first.
- 3) OS is defined as the time from start of treatment to death due to any cause. Participants without documented death at the time of the analysis will be censored at the date of last follow-up. See Section 9.6.2 for the definition of censoring.

#### **9.4.3 Safety Endpoints**

Refer to Section 4.2.1.2 for the description of the safety measures.

### **9.5 Analysis Populations**

#### **9.5.1 Biomarker Analysis Population**

The All Participants as Treated (APaT) population will be used for the analysis of biomarker endpoints. The APaT population consists of all allocated participants who received at least one dose of study treatment. For analysis related to post-baseline biomarker values, at least one post-baseline measurement is required for inclusion in the analysis of each specific biomarker endpoint.

#### **9.5.2 Efficacy Analysis Population**

The APaT population will be used for the analysis of ORR, PFS and OS. Details on the approach to handle missing data are provided in Section 9.6 Statistical Methods.

#### **9.5.3 Safety Analysis Population**

The APaT population will be used for the analysis of safety data in this study. At least one laboratory or vital sign measurement obtained subsequent to at least one dose of study treatment is required for inclusion in the analysis of each specific parameter. To assess change from baseline, a baseline measurement is also required.

## 9.6 Statistical Methods

For the primary study objectives enumerated in Section 3, the overall analysis strategy is to formulate reasonable parametric models for the distributions of the measures describing the nature and frequency of cytotoxic tumor-infiltrating T-lymphocytes. These models, formulated in a Bayesian framework, will be used to understand the differences for responders vs. non-responders by evaluating and comparing their posterior distributions of the model parameters. Details are described in Section 9.6.1.

Analyses methods for efficacy and safety endpoints are described in Section 9.6.2 and Section 9.6.3, respectively.

### 9.6.1 Statistical Methods for Biomarker Analysis

This section describes the statistical methods that address the primary objectives. Data will be examined for departures from the assumptions of the distribution model(s) as appropriate. Suitable data transformation may be applied if a serious departure from the assumptions of the model(s) is observed, or other suitable distributions may be used in the Bayesian models.

Methods related to secondary and/or exploratory biomarker related objectives may be described in sSAPs.

#### *Baseline FCT*

To address the first primary objective, the difference in mean baseline FCT between responders and non-responders will be quantified by calculating the posterior probability that the mean baseline FCT for responders exceeds that of non-responders, under a Bayesian model assuming the participant FCTs arise from a Beta distribution. Non-informative (vague) priors will be used: e.g., a Uniform (0, 1) prior for both the means of responders and non-responders. The first primary hypothesis will be supported if the posterior probability that the mean baseline FCT for responders exceeds that of non-responders is greater than 70%. The 95% posterior credible interval will also be provided for the difference in the mean baseline FCT between responders and non-responders.

Supportive analyses may be performed by comparing the average baseline *CytS* scores of the two populations by using a hierarchical linear model (HLM) that captures the hierarchical structure of the data.

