#### *FCT Fold Change from Baseline*

Individual FCT fold change from baseline values will be natural log transformed prior to statistical analysis. It is expected that the mean FCT log fold-change from baseline in responders is higher than that in non-responders. The difference in mean FCT log fold-change from baseline between responders and non-responders will be quantified by calculating the posterior probability that the difference exceeds zero under the Bayesian framework. The planned approach will be to assume that these participant-level FCT log fold-change from baseline values arise from normal distributions with means and variances that potentially differ for responders and non-responders. Non-informative (vague) priors will be used: e.g., a diffuse normal distribution centered at 0 with precision 1e-06 as prior for the mean, and a Gamma (1e-04, 1e-04) distribution as prior for the precision. The same priors will be used for both responders and non-responders. The second primary hypothesis

will be supported if the posterior probability that the mean FCT log fold-change from baseline of responders exceeds that of non-responders is greater than 70%. The 95% posterior credible interval will also be provided for the difference in mean FCT log fold-change from baseline between responders and non-responders.

Supportive analysis may be performed by adding to the hierarchical linear model a covariate time point to indicate whether the sample was taken before or after treatment, and an interaction term between the response and time point.

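### FCT can be exactly zero; the Beta likelihood and the log fold-change cannot use a zero, and the SAP fixes no rule for one

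*Combined protocol and SAP*

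**What the plan says.** Section 9.4.1.1 defines FCT as "the number of cytotoxic CD8+ T-cells (with high cytotoxic scores) divided by the number of total CD8+ T-cells that were sequenced in this tumor". A cell counts as cytotoxic if its score lies above a natural cutoff when the scores are bimodal. Otherwise it must pass an artificial "cutoff using the continuous scores (e.g., 90th percentile"). The section does not say whether that percentile is pooled over tumors or taken within each one.

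Section 9.6.1 then sets the primary methods. Baseline FCT is compared "under a Bayesian model assuming the participant FCTs arise from a Beta distribution" with, as an example, "a Uniform (0, 1) prior for both the means of responders and non-responders"; no prior is given for the precision. For the second endpoint, "Individual FCT fold change from baseline values will be natural log transformed prior to statistical analysis", and the values are modelled as normal. Each hypothesis is supported if the posterior probability that responders have the higher mean exceeds 70%.

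The nearest provision for awkward data is the opening of Section 9.6.1. If a serious departure from assumptions is observed, a transformation may be applied or "other suitable distributions may be used in the Bayesian models". The hierarchical models on cytotoxicity scores would avoid zeros, but they are optional: "Supportive analyses may be performed by comparing the average baseline" scores, and for change, "Supportive analysis may be performed by adding to the hierarchical linear model a covariate time point". Section 9.5.1 requires one post-baseline measurement and is silent on a measured zero. No section gives a minimum CD8+ cell number.

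**The concern.** A tumor with some CD8+ cells but none above the cutoff has FCT = 0. At that point a Beta density is infinite (alpha below 1) or zero (alpha above 1), so the baseline likelihood breaks down. The log fold-change is undefined or infinite if either FCT is zero. Two of the three primary endpoints are therefore tied to methods that fail on values their own definition allows.

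Someone will have to choose a rule, and the text lets that happen after the data are seen. Dropping zeros removes participants according to their FCT, the quantity under study. Adding 0.5 to the counts keeps them, but makes the answer depend on how many cells each biopsy yielded. Either choice can decide whether the fold-change hypothesis is called supported. ASCTFR (Section 9.4.1.1) has the same gap on a log10 scale for a clone undetected at one time point; how often that occurs cannot be derived from the documents.

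**Working it through.** **Inputs.** From Section 9.9.1:
- Non-responder baseline FCT is Beta(0.022, 1), mean 0.022/1.022 = 0.0215.
- Responders at difference 0.10 have mean 0.1215, so alpha = 0.1215/0.8785 = 0.1383 with beta fixed at 1.
- The threshold is 70% (normal quantile 0.524). Table 10 uses an SD of 1.

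Assumed, because the documents do not give them:
- CD8+ cells per biopsy, n = 50 to 10,000.
- Two gentler distributions: Beta(1, 28.4), which also puts 1 - 0.9^28.4 = 95% below 0.10, and Beta(1, 9), whose mean of 0.10 is what a pooled 90th-percentile cutoff would give.

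**Plan's own figures.** P(FCT < 0.10) = 0.10^0.022 = 95.1%, as stated. Table 10, 10 v 50, effect 0.50: Phi(0.5/sqrt(1/10 + 1/50) - 0.524) = Phi(1.443 - 0.524) = 82%, against the stated 81%. Simulating the unequal-variance model reproduces all six cells within 2 points. Table 9 reproduces only in part; its precision prior is not stated, so it is not called wrong.

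**Share of zero baselines.** For Beta(a, 1), P(k = 0) = Gamma(a+1)Gamma(n+1)/Gamma(a+1+n). For Beta(1, b), it is b/(b+n).

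| n | Non-responders, planning | Responders, planning | Beta(1, 28.4) | Beta(1, 9) |
|---|---|---|---|---|
| 50 | 91% | 55% | 36% | 15% |
| 100 | 89% | 50% | 22% | 8% |
| 500 | 86% | 40% | 5% | 2% |
| 10,000 | 81% | 26% | 0.28% | 0.09% |

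At a 30% response rate, the planning inputs give zero baselines in 80% of all participants at 50 cells (0.7 x 0.906 + 0.3 x 0.545) and 64% at 10,000.

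**Fold-change power if zero baselines are dropped** (10 v 50, effect 0.50, SD held at 1). At 100 cells under planning inputs, 10 x 0.505 = 5.05 responders and 50 x 0.108 = 5.4 non-responders remain, so power is Phi(0.5/sqrt(1/5.05 + 1/5.4) - 0.524) = 61%. At 500 cells it is 65%, and at 10,000 cells 69%. Under the gentler distributions it is 77% and 80% at 100 cells, and 81% and 82% at 500.

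**Does the rule change the decision?** Counts were simulated as binomial with p1 = p0 x exp(d) and d having SD 1 before counting noise, then analysed with the normal model of Section 9.6.1 (10 v 50, effect 0.50, equal yield, 1,500-2,000 trials). Dropping a zero at either time and adding 0.5 to both counts disagree on support in about 36% of trials at 100 cells and 28% at 500 (planning), or 6-25% over the same range (gentler).

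**Support with no true change** (nominal 30%; 18 v 42; planning inputs with the 0.10 baseline difference; cells at baseline/on treatment):
- Add 0.5 to the counts: 31% at 100/100, about 62% at 100/150, about 80% at 100/200, 3% at 200/100. The reason is visible by hand: a pair that is zero at both times gets log(n0/n1), which is log(100/200) = -0.69 from yield alone, and most such pairs are non-responders.
- Add 0.005 or 0.01 to FCT itself at both times: about 28-36% at the same pairs, because a zero/zero pair then scores 0 at any yield.
- The 0.5 offset stays at 27-33% if both groups share a gentler baseline, and ranges over 14-38% if Beta(1, 28.4) differs by 0.10 between groups.

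**Baseline FCT** (10 v 50, 100 cells, difference 0.10). Replacing zeros by small values gives about 91% power, and dropping them about 42%. A beta-binomial with a uniform 0-500 precision prior gives 70% and 90% at differences 0.05 and 0.10, against Table 9's 68% and 90%. The precision prior matters. With no true difference, support is 22-31% under that prior, 33-39% under a log-uniform prior and 26-50% under Gamma(1, 0.1).

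**The case against.** The strongest case against is that the plan leaves room for a simple answer. Section 9.6.1 permits a transformation or another distribution, Section 9 routes changes before database lock through a supplemental SAP, Section 9.2 has assays run blinded to outcome as appropriate, and Section 9.8 calls all analyses exploratory. Section 9.5.1 also points towards keeping zeros, since a measured zero is a measurement, and at equal yield the rules that keep zeros disagree with each other in fewer than one trial in ten. All of this stands and limits the weight of the point. It does not close the gap: no rule is named, the permission starts only once a departure is seen, and a fixed 70% criterion is still applied to each primary hypothesis.

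Two stronger readings do not hold. A reader might infer that every fixed offset is unsafe. The bad false-support figures belong to a constant added to raw counts; a constant on the FCT scale stays near 30% under the planning inputs. A reader might also infer that fold-change must be analysed with a hierarchical count model. At 100 cells and effect 0.50, planning inputs, such a model gave support in about 49% of trials against 65-67% for an FCT-scale offset. It relies on an approximation for FCT well below 1, and it needs informative priors in place of the SAP's vague ones.

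**Conclusion.** The point holds and should be fixed. That zeros are possible follows from the definition alone; the one exception is a percentile cutoff taken within each tumor, which would hold FCT near 0.10 everywhere and leave nothing to compare. That the stated methods cannot use a zero is a mathematical fact.

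The size is uncertain. It would be tempting to say that four in five participants or more will have zero FCT. The documents do not support this as a forecast: Beta(0.022, 1) is a power input with a median near 2e-14, and no cell number is given. Under the gentler distributions with 500 or more cells, the problem nearly vanishes.

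Nor does the check show that baseline FCT power is lost or that Table 10 is wrong. Baseline power is little affected if zeros are kept, and Table 10 reproduces on its own terms. The rule comparisons put counting noise on top of an SD of 1, so they rank rules against each other and not against Table 10. What is exposed is the fold-change decision, through an unstated choice between dropping zeros and keeping them, and through the form of any constant added.

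**What to change.** 1. **Baseline FCT (Section 9.6.1).** Replace the Beta likelihood with a beta-binomial: k of n CD8+ cells is binomial with probability p, and p is Beta by response group. Keep the Uniform(0, 1) priors on the means and state a precision prior, for example uniform from 0 to 500.
2. **FCT fold-change (Section 9.6.1).** Fix one rule before anyone handling FCT sees response status. Keep measured zeros and do not add a constant to raw counts. Either use a stated small constant on the FCT scale, the same at both time points, or a count model with stated priors as a sensitivity analysis. With the constant, say that the estimand is the change in log(FCT + constant). Its calibration is not perfect: with Beta(1, 28.4) and a 0.10 baseline difference, support under no change was 20-27%.
3. **Cutoff (Section 9.4.1.1).** Say whether the percentile is pooled or per tumor.
4. **ASCTFR.** State how a clone undetected at one time point is treated.
5. **Tables 9 and 10.** Re-run them on simulated counts over a stated range of cell numbers, and say whether the SD of 1 includes counting noise.

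The cost is SAP or supplemental SAP wording, a little coding and two re-run tables, with no new data. The baseline change costs no power in the check above. The fold-change power figure may come out lower, most clearly under the count model, because participants with zero at both times carry no information on change.
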